5.4 Survival follow-up

If a subject is no longer indicated for TACE, they will enter survival follow-up. During survival follow-up, subjects are contacted every three months (\pm 2 weeks) to determine their survival status. Subjects can be contacted (via phone, email, written response), their medical records reviewed, and/or information can be obtained from additional sources (i.e., the subject's caregivers/family members) to determine if the subject is alive. These survival contacts should continue until one of the following conditions is met:

- Subject dies
- Subject withdraws consent

- Subject is classified as lost to follow-up

Lost to follow-up (LTFU): All reasonable efforts will be made to obtain complete data for all subjects. Missing observations from unsuccessful contact attempts will occur due to some subjects being LTFU, having withdrawn from the study, or not adhering to required assessments. Three (3) total attempts shall be made to contact a subject. If a subject cannot be accounted for (i.e., by visit, telephone call, email, written response, family member report, etc.) and has not followed-up accordingly with the clinical site, they will be considered lost to follow-up. Study data collected on this subject, up to the date and time of loss to follow-up (or subject withdrawal) will remain in the study database and used for analysis purposes, as appropriate. These subjects will not be replaced. Survival follow-up information will be collected within the electronic database capture (EDC) system.

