7.1 Primary Efficacy Analyses

Median Overall Survival

The primary efficacy analyses of median overall survival will be performed when all subjects enrolled have reached two years of long-term survival follow up or have died, whichever comes first.

Survival time will be calculated (in months) utilizing the date of the first TACE procedure and the date of death (from any cause), or lost to follow up.

Median overall survival times will be calculated using the Kaplan-Meier (product-limit) method and corresponding 95% confidence intervals will be generated. One- and two-year survival rates and corresponding 95% confidence intervals will also be calculated.

In order to assess the consistency of observed treatment effect across investigational sites, a data poolability analysis will be performed on the primary efficacy outcomes of overall survival. Median overall survival data will be summarized by site, including Kaplan-Meier plots.

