4. OUTCOME VARIABLES

4.1. PRIMARY OUTCOME

Patient survival will be calculated in months from the date of the first TACE procedure until a date of death is obtained or the subject is lost to follow up (utilizing the last successful contact with the patient). Median overall survival time will be the primary outcome of the study.

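### Loss to follow-up ends survival contacts and no later vital-status check is required, so unascertained deaths would be censored and could inflate median overall survival

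*Protocol*

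**What the plan says.** Protocol 5.4 sets the survival contacts: "subjects are contacted every three months", with a two-week window either side. It then lists what ends them ("These survival contacts should continue until one of the following conditions is met"): death, withdrawal of consent, or "Subject is classified as lost to follow-up".

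On how a subject reaches that class, the section says "Three (3) total attempts shall be made to contact a subject". The next sentence adds two conditions. The subject cannot be accounted for by visit, telephone, email, written reply, family report or similar, "and has not followed-up accordingly with the clinical site, they will be considered lost to follow-up". Neither the spacing of the attempts nor whether the count restarts at each scheduled contact is stated.

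The same section lets the site establish vital status without reaching the subject. Subjects may have "their medical records reviewed, and/or information can be obtained from additional sources", such as caregivers or family. These sources are permitted, not required.

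SAP 2.1 says that all enrolled and treated subjects are followed for survival until the data analysis.

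On the censoring date, Protocol 2.1 and SAP 1.1 use the last successful contact, as does SAP 4.1: "the subject is lost to follow up (utilizing the last successful contact with the patient". Protocol 7.1 has survival time calculated "utilizing the date of the first TACE procedure and the date of death (from any cause), or lost to follow up", with no mention of last contact.

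The analysis is a Kaplan-Meier median with 95% confidence interval, plus 1- and 2-year rates (Protocol 7.1, SAP 5.2). SAP 5.1 rules out imputation. Neither document plans a sensitivity analysis for losses.

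**The concern.** Kaplan-Meier treats a censored subject as having the same later risk as those still followed. That may fail here. Survival follow-up starts when a subject is no longer indicated for TACE (Protocol 5.4), the disease is metastatic and unsuitable for resection or ablation, and the entry criterion for life expectancy is only 3 months or more (Protocol 4.1). It is a reasonable inference, though not a statement in the documents, that some subjects become unreachable because they have declined or died.

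Because classification ends the contacts, a death after that point need never be found, however careful the search was at the time. Median overall survival is the single primary endpoint, no control arm shares the error, and the result will naturally be read against the earlier cohorts summarised in Protocol 1.0. The confidence interval would not reflect the error.

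**Working it through.** There is no plan figure to reproduce. The minimum of 100 subjects was chosen by similarity to earlier studies (Protocol 7.0, SAP 2.5), without a precision target or loss rate.

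**Inputs**
- Contact interval: 3 months (Protocol 5.4).
- N = 100 + 5 = 105 (SAP 2.1).
- Scenario median m = 19 months, from the US cohort cited in Protocol 1.0. It serves only as an example.
- q, the share of deaths that are never ascertained and are recorded as losses: not given in the documents, so assumed at 5%, 10% and 20%.
- Exponential survival: assumed.

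**Closed form.** The death hazard is λ = ln 2 / m. If a share q of deaths is turned into censorings near the date of death, the observed hazard is (1 − q)λ. The apparent median is then m/(1 − q), and apparent survival at t months is 2^(−(1 − q)t/m).

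**Check by simulation.** 200,000 subjects; analysis cut-off at 24 months plus a uniform 0 to 36 months (assumed accrual spread); unreached deaths censored at the preceding 3-monthly contact.

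| q | m/(1 − q) | Simulated median | 24-month rate, closed form | 24-month rate, simulated |
|---|---|---|---|---|
| 0 | 19.0 | 18.9 | 2^(−24/19) = 41.7% | 41.6% |
| 5% | 19/0.95 = 20.0 | 20.0 | 2^(−0.95×24/19) = 43.5% | 43.6% |
| 10% | 19/0.90 = 21.1 | 21.0 | 2^(−0.90×24/19) = 45.5% | 45.2% |
| 20% | 19/0.80 = 23.75 | 23.5 | 2^(−0.80×24/19) = 49.6% | 49.3% |

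The 1-year rate at q = 10% moves from 2^(−12/19) = 64.5% to 2^(−0.90×12/19) = 67.4%.

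**What q means in subjects.** With N = 105 and m = 19, expected deaths by month 24 are 105 × (1 − 0.417) ≈ 61. So q = 5%, 10% or 20% corresponds to about 3, 6 or 12 unreached deaths by then.

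**If loss is unrelated to death.** With the same probabilities of loss before death (5%, 10%, 20%), the simulated median is 18.95, 18.87 and 18.83 months. There is no upward shift.

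**Censoring date.** Censoring unreached deaths at the next contact, when the loss is noticed, gives 20.1, 21.2 and 23.95 months instead of 20.0, 21.0 and 23.5. The difference is about 0.1 to 0.4 months.

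**Reaching the median.** If everyone were cut at exactly 24 months (N = 105, m = 19), the chance that the median is not reached rises from 4.5% at q = 0 to 17.4% at q = 10% and 43.9% at q = 20%.

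**Sampling error for scale.** At N = 105 and m = 19, the 95% sampling range of the median is about 14.1 to 24.5 months.

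**The case against.** Several stronger readings are tempting, and the documents do not support them.

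- *Three failed attempts end follow-up by themselves.* They do not. The subject must also be unaccounted for by any route, including family report, and must not have followed up with the site. A death known to the family or the hospital should be found before classification. This limits q but does not make it zero: record review is optional, and a search at classification cannot find later deaths.
- *The three attempts cover the whole study.* The word total allows that reading, but a study-wide cap of three fits poorly with about eight quarterly contacts over 24 months (24/3 = 8). The text is ambiguous.
- *Lost subjects are never checked again.* Nothing forbids it. Protocol 5.4 promises all reasonable efforts, and SAP 2.1 speaks of survival follow-up until analysis. However, SAP 2.1 ties the timing of the analysis to subjects actively followed, and SAP 1.1 accepts loss as an endpoint of follow-up. The passages are in tension, and no re-check is required.
- *The median is biased.* That depends on a loss rate and a link to death that the documents do not give. The table takes every loss to be a death, which is the unfavourable extreme.
- *The documents give two different censoring dates.* Protocol 7.1 may simply be shorter wording, and the effect is small.

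It is also fair to say that the shifts at q = 5% or 10% lie well within sampling error. But sampling error is reported in the interval and this error is not. A further caution is that deaths may be easier to find in records than survival, so a one-sided search could bias the median downwards.

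**Conclusion.** The point holds in conditional form. Followed as written, the plan allows unascertained deaths to be censored in the primary analysis, with no required re-check and no sensitivity analysis to show the effect. If losses are unreached deaths, the median is inflated by about m × q/(1 − q): for m = 19 months, roughly 1, 2 or 4.5 months at q = 5%, 10% or 20%. If losses are unrelated to death, there is no upward bias. These sizes rest on assumed q, exponential survival and an assumed accrual spread; the documents support the mechanism, not a particular value. This is a cheap improvement, not a flaw that invalidates the study.

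**What to change.** - Protocol 5.4: require one vital-status check at a common cut-off date before database lock, for every subject not known to be dead who has not withdrawn consent, using the sources the section already allows (medical records, caregivers or family). Covering all such subjects, and seeking evidence of survival as well as of death, guards against a one-sided search.
- Reconcile Protocol 5.4 with SAP 2.1 on whether lost subjects are followed until analysis.
- Protocol 5.4: state that the three attempts apply to each scheduled contact. Protocol 2.0 reports at least 100 patients already treated, so this helps only contacts still to come; the cut-off check helps regardless.
- Use one censoring date, the last date known alive from any allowed source, in Protocol 2.1 and 7.1 and SAP 1.1 and 4.1. This changes the SAP wording too, since last successful contact differs from last known alive when the information comes from records or family.
- For subjects still unknown, report the number and add a sensitivity analysis that treats loss as death at or soon after last contact. It is deliberately pessimistic; beside the main analysis it shows how much the result depends on these subjects.

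The cost is one round of record review or calls at two hospitals, one of which holds 100 of the 105 subjects, plus wording changes and one extra analysis. The reported median may be slightly less favourable.

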6.0 Treatment-Related Adverse Events

Treatment-related adverse events are defined in this study as any event that began on or after the date of the first TACE procedure or worsened in severity and/or frequency after the first TACE procedure was initiated and is considered related to the TACE procedure by the investigator. Events worsening in severity will be considered new adverse events. All related events must be reported in the case report form and followed until resolution.

6.1 Severity of Treatment-Related Adverse Events

The Investigator, based on their clinical judgment and the following definitions, must determine the severity of the adverse event (AE):

- Mild: asymptomatic or mild symptoms; clinical or diagnostic observations only; intervention not indicated
- Moderate: minimal, local, or noninvasive intervention indicated; limiting age-appropriate instrumental activities of daily living
- Severe or medically significant but not immediately life-threatening: hospitalization or prolongation of hospitalization indicated; disabling; limiting self-care activities of daily living
- Life-threatening consequences: urgent intervention indicated
- Fatal

6.2 Relationship of Adverse Event to Treatment (Device and/or Procedure)

The Investigator, based on their clinical judgment and the following definitions, must determine the relationship of the adverse event to the device and/or procedure:

- Possible: The AE/SAE follows a reasonable temporal sequence from the time of TACE procedure, and/or follows a known response pattern to the TACE procedure but could have been produced by other factors
- Probable: The AE/SAE follows a reasonable temporal sequence from the time of TACE procedure, follows a known response pattern to the TACE procedure, and cannot reasonably have been produced by other factors
- Definite: The AE/SAE follows a reasonable temporal sequence from the time of TACE procedure; follows a known response pattern to the TACE procedure; and cannot have been produced by other factors.

6.3 Reporting of Treatment Related Serious Adverse Events (SAEs)

Any treatment-related SAE that occurs on or after the date of the TACE procedure or worsened in severity or frequency after the TACE procedure must be reported to the Sponsor immediately (not to exceed 24 hours within site notification of the event) in the eCRF or via email. It is the responsibility of the Investigator(s) to inform their EC of complications or serious injury as required

Merit Medical Systems, Inc.**CRC-P4-16-01 (V2.0), dated 21 Apr 2021**

Administrative change 21 APR 2021

by their EC procedure(s) and/or applicable regulations. Merit Medical is responsible for relaying information about serious adverse events and/or treatment related adverse events to the other participating Investigators and regulatory bodies as required.

7.0 Statistical Analysis

Sample Size

This prospective registry is observational and single arm, so there are no cohorts on which to perform comparisons or sample size calculations. A minimum sample size of 100 patients was chosen as being similar in size to studies conducted by Aliberti (N=82) and Fiorentini (N=74) for a similar product CE marked for the same indication.

Analysis Population

All patients who have at least one TACE procedure will be included in the safety analyses. All patients who have at least one TACE procedure and who have at least one post-baseline tumor evaluation will be included in the efficacy analyses.

7.1 Primary Efficacy Analyses

Median Overall Survival

The primary efficacy analyses of median overall survival will be performed when all subjects enrolled have reached two years of long-term survival follow up or have died, whichever comes first.

Survival time will be calculated (in months) utilizing the date of the first TACE procedure and the date of death (from any cause), or lost to follow up.

Median overall survival times will be calculated using the Kaplan-Meier (product-limit) method and corresponding 95% confidence intervals will be generated. One- and two-year survival rates and corresponding 95% confidence intervals will also be calculated.

In order to assess the consistency of observed treatment effect across investigational sites, a data poolability analysis will be performed on the primary efficacy outcomes of overall survival. Median overall survival data will be summarized by site, including Kaplan-Meier plots.

7.2 Secondary Efficacy Analyses

Objective Response Rate

Objective Response Rate (ORR) will be based on the last post-TACE liver MRI or CT response recorded for each patient, as determined by mRECIST criteria. ORR will be calculated for the efficacy population as the number of patients with a confirmed complete or partial response (based on mRECIST criteria) divided by the number of patients [ORR=(# CR + # PR)/total # patients]. Ninety-five percent confidence intervals will be calculated.

Best Tumor Response

An informative analysis of best tumor response in the period from treatment initiation through the date of the last post TACE liver MRI or CT, based on mRECIST criteria, will be summarized as the number and percentage of patients in each response category (complete response, partial response, stable disease, progression) for the effectiveness population.

Median Liver Progression-free Survival

Median liver progression-free survival (PFS) will be calculated (in months) from the date of the first TACE procedure to the date of diagnosis of colorectal cancer liver metastasis to the date of death, or date last known to be alive for patients who are lost to follow up, during which follow up imaging

Merit Medical Systems, Inc.**CRC-P4-16-01 (V2.0), dated 21 Apr 2021**

Administrative change 21 APR 2021

by MRI or CT demonstrates a lack of tumor progression in the liver as determined by mRECIST criteria. Corresponding 95% confidence intervals will be generated.

Time to Progression

Time to progression (TTP), including progression of extrahepatic disease, will be calculated in months from the date of the first study TACE procedure until the date of disease progression, determined by MRI, CT, PET scan, or equivalent imaging. Corresponding 95% confidence intervals will be generated.

Safety Summary

Safety summaries will include the incidence of treatment-related adverse events in patients who had at least one TACE embolization. Treatment-related adverse events are defined as any event that began on or after the date of the first embolization or worsened in severity or frequency after embolization was initiated, and are evaluated as possibly, probably, or definitely related to study treatment by the investigator. Events worsening in severity will be considered new adverse events.

7.3 Additional Analyses

Pharmacokinetic (PK) Analyses

PK blood samples drawn from a portion of the subjects after the first TACE cycle (at four pre-determined time periods) will undergo bioanalytical analysis using validated assays. The assays will measure the subject's plasma concentrations of irinotecan and its active metabolite, SN38. Data will be summarized by descriptive statistics, including mean, standard deviation, coefficient of variation, minimum, maximum, and median. The correlation between circulating levels of irinotecan and SN38 and overall survival, tumor response, and treatment-related adverse events will be evaluated to the extent possible with the available PK data.

Additional TACE Cycles

Overall survival time will be compared between standard TACE cycles and additional TACE cycles (any TACE procedure(s) beyond the protocol specified TACEs) using Kaplan-Meier estimator with log-rank testing. Comparison of additional TACE cycles between tumor response will be performed using Fisher's exact test.

RECIST 1.1

Clinical outcomes will be reanalyzed based on RECIST 1.1 criteria. The best tumor response will be compared between mRECIST and RECIST 1.1 using Fisher's exact test.

Clinical Success

Similar to ORR, clinical success will be based on the last post TACE liver response evaluated through mRECIST and RECIST 1.1 criteria. Clinical success is defined as the total number of confirmed subjects who exhibit a complete or partial response [clinical success = (# CR + #PR)].

8.0 Withdrawal of Patients

Patients will be informed that they have the right to withdraw from the study at any time for any reason, without prejudice to their medical care. The investigator also has the right to withdraw patients from the study for any of the following reasons:

- Adverse events
- Disease progression
- Non-compliance with study requirements

Merit Medical Systems, Inc.**CRC-P4-16-01 (V2.0), dated 21 Apr 2021**

Administrative change 21 APR 2021

If a patient withdraws consent or is discontinued from the study, the reason will be recorded in the source documents and in the CRF.

9.0 Data Recording and Retention

Data will be abstracted from medical records from standard of care treatment reports. Data will be entered into an electronic data capture system and retained electronically for a minimum of 15 years after the completion of the registry or longer per the sponsor's request.

10.0 Good Clinical Practice

This study will be conducted in accordance with the International Conference on Harmonization (ICH) E6 for Good Clinical Practice (GCP): Consolidated Guidance and the appropriate regulatory requirement(s). The investigators will be thoroughly familiar with the appropriate use of the treatment procedure as described in the protocol. Protocol deviations will be summarized in the final clinical study report. Essential clinical documents will be maintained to demonstrate the validity of the study and the integrity of the data collected.

11.0 Ethical Considerations

The study will be conducted in accordance with ethical principles founded in the Declaration of Helsinki. The Ethics Committee (EC) will review all appropriate study documentation in order to safeguard the rights, safety, and well-being of the patients. The study will only be conducted at sites where the EC approval has been obtained. The protocol, informed consent, advertisements (if applicable), written information given to the patients, safety updates, annual progress reports, and any revisions to these documents will be provided to the EC by the investigator.

12.0 Patient Confidentiality

In order to maintain patient privacy, each patient will be given a unique registry number. All CRFs and registry reports will identify the patient only by the assigned patient number. This anonymized data will be stored in a secure electronic database with access at the site limited to physicians and registry staff who have password and username for log in to the system. Only registry site staff will know the patient name correlated to the registry identification number for each participant. The Investigator will grant monitor(s) and auditor(s) from Merit Medical or its designee and regulatory authority(ies) access to the patients' original medical records for verification of data gathered on the CRFs and to audit the data collection process. The patients' confidentiality will be maintained and will not be made publicly available to the extent permitted by the applicable laws and regulations.

APPENDIX A

Schedule of Procedures

	Screening ¹	TACE Procedure ²	Follow Up Visits ³	Survival Follow-up ⁴
Informed Consent	X			
Eligibility criteria assessment	X			
Demographics	X			
Medical History	X			
Tumor Evaluation / Imaging	X		X	
Hematology / Serum Chemistry	X			
Embolization procedures (TACE)		X		
Pharmacokinetic Sampling ⁵		X		
Additional cancer treatments			X	
Adverse Events		X	X	
Survival status				X

¹ Screening imaging must be within 4 weeks of first TACE cycle.

² First TACE cycle must be within 4 weeks of screening imaging. If the patient has bilobar disease, the embolization of the first lobe must be within 4 weeks of screening imaging and the second lobe must undergo embolization within 3 weeks (\pm 2 weeks) of the first lobe. A second TACE cycle is required for all patients 2-4 weeks after the first TACE cycle. Additional TACE cycles can be performed for residual or new disease as needed.

³ Follow up Visits will start 4-6 weeks after the second TACE cycle and occur every 12 weeks (\pm 2 weeks) thereafter during the first year of follow-up. Follow-up may be more frequent if medically indicated.

⁴ If patients are no longer indicated for TACE, they will continue to be followed for survival for 2 years after the first TACE procedure, with contacts performed every 3 months (\pm 2 weeks).

⁵ Blood samples will be drawn for PK analysis from a portion of study patients after the first TACE procedure at the following time points; 30 min, 1 hour, 4 hours, 12 hours, and 24 hours or prior to discharge (whichever comes first).

